6.2 Handling of Dropouts, Missing Data, and Outliers

Missing data will not be imputed for safety analyses. The safety evaluations will be performed on observed data only.

For AEs with partial or missing onset or stop dates:

AE stop date will be imputed first as:

- If stop date is complete missing, assume it is ongoing (no imputation);
- For a partial AE stop date (day is missing, or both day and month are missing): December 31st if both day and month are missing, or last day of the month if only day is missing.

Then AE onset date will be imputed as:

- If onset date is complete missing: the first dose date;
- For a partial AE onset date (day is missing, or both day and month are missing):
 - Partial date < the first dose date: December 31st, or last day of the month
 - Partial date = the first dose date: the first dose date
 - Partial date > the first dose date: January 1st if both day and month are missing, or first day of the month if only day is missing.

If the imputed AE onset date is after the AE stop date/imputed AE stop date, then the onset date will be set to the AE stop date/imputed AE stop date.

The imputed dates will not be listed. Study day relative to the first dose of double-blind study drug associated with missing or partial dates will not be displayed in AE listings.

In the event that a partial date (month/year or year) for concomitant medication is available, this information will be used as follows:

- When both month and year are available – first day of the month will be used for start date and the last day of the month will be used for the stop date.
- When only year is available – January 1st will be used for the start date and December 31th will be used for the stop date.

The imputed dates will only be used to determine whether a concomitant medication will be classified as prior medication or concomitant medication.

6.2.1 Observed Cases Datasets

Mixed-effects model for repeated measurements (MMRM) will be performed based on a missing at random (MAR) assumption using data actually observed - observed cases (OC) dataset. OC datasets will be used for analysis of the primary efficacy as well as all secondary efficacy endpoints. This dataset will not impute any values for missing observations.

7. Statistical Methods

7.1 General Principles

All data processing, summarization and analyses will be performed using the Hosted SAS (d-Wise) Environment / Version 9.4 (or later) of the SAS[®] (SAS Institute, Cary, NC) statistical software package.

Unless specified otherwise, data will be displayed using the following treatment group labels, in the order presented:

- Placebo
- TMX-049 40 mg QD
- TMX-049 200 mg QD
- TMX-049 Overall

All data collected will be presented in listings by treatment group, center, subject, and visit (where applicable), unless otherwise specified.

Data will be presented in summary tables by treatment group, assessment, and visit (where applicable).

The category "Missing" will be presented if the number missing is greater than zero for at least 1 treatment group.

Descriptive summary statistics for continuous variables will include the number of observations (N), mean, standard deviation (SD), median, minimum, and maximum. For UACR of original scale, the geometric mean, geometric coefficient of variation (CV), and CV will also be provided.

Descriptive summary statistics for categorical variables will include frequency counts and percentages [n (%)]. Unless stated otherwise in the table shells, the denominator for percentage calculations will be the number of subjects in the pertinent analysis population.

Dates will be displayed as DDMMYYYY.

Analysis and summarization of treatment group comparisons for the primary and secondary efficacy endpoints will be reported in their original measurement units and converted values to accommodate regulatory review by FDA and external authorities, where appropriate.

All significance tests will be 2-sided and use a 0.05 α -level.

7.2 Subject Disposition and Data Sets Analyzed

Subject disposition will be listed and summarized by treatment group, and will include the number and percentage of subjects:

- Screened
 - Entered single-blind Placebo run-in period
 - Discontinued single-blind Placebo run-in period
-

- Randomized
- Treated
- Included in each study population (All subjects, Randomized, mITT, Safety, PP, and PK)

The number and percentage of subjects who complete the study and those who discontinue early (including a breakdown of the primary reasons for discontinuation), will be presented for the subjects randomized in each treatment group.

A summary of subject enrollment by site will be provided by treatment group and overall. A summary of subject randomized by randomization strata (sUA and UACR levels) will also be provided by treatment group.

7.3 Protocol Deviations

All the important protocol deviations leading to exclusion from the PP population will be listed and summarized by treatment group for the mITT population.

7.4 Demographics and Other Baseline Characteristics

Demographic and baseline characteristics will be listed and summarized by treatment group for the mITT, Safety, and PP population. Standard descriptive statistics will be presented for the continuous variables of:

- Age at study entry (years)
- Weight (kg)
- Height (cm)
- Body mass index (BMI) (kg/m^2)
- Supine systolic blood pressure (SBP) (mm Hg)
- Supine diastolic blood pressure (DBP) (mm Hg)
- Pulse rate (beats/min)
- Temperature ($^{\circ}\text{C}$)

The total counts and percentages of subjects will be presented for the categorical variables of:

- Age group (years) (<65; \geq 65)
- Sex (Male; Female)
- Race
- Ethnicity
- BMI categories (\leq 30 kg/m^2 ; $>$ 30 kg/m^2)
- Tobacco use (Yes, number of cigarettes/day; No)

- Alcohol Drinking (Yes, number of units/week; No)

Baseline laboratory characteristics for a select number of tests will also be summarized by treatment group for the mITT, Safety, and PP population. Standard descriptive statistics will be presented for the following laboratory tests:

- Urinary albumin-to-creatinine ratio (UACR) (mg/g)
- Log-transformed UACR (mg/g)
- HbA1C (%)
- eGFR (CKD-EPI) (ml/min/1.73m²)
- Serum creatinine (mg/dL)
- Serum uric acid (mg/dL)
- Total cholesterol (mg/dL)
- High-density lipoprotein cholesterol (HDL-C) (mg/dL)
- Non-HDL-C (mg/dL)

A summary of physical examination data will be presented by treatment group for the mITT, Safety, and PP population.

No formal tests of statistical significance will be performed on the demographic and Baseline data.

7.4.1 Medical History

Medical history will be coded using the Medical Dictionary for Regulatory Activities (MedDRA) Version 20.5 (or a later version if updated during the study). All medical history will be listed, and the number and percentage of subjects with any medical history will be summarized for the mITT population by system organ class (SOC) and preferred term (PT) for each treatment group.

7.4.2 Previous and Concomitant Medications

Medications received prior to or concomitantly with treatment will be coded by [REDACTED] using the World Health Organization (WHO) Drug Dictionary, Version September 2017 (or a later version if updated during the study), Anatomical Therapeutic Chemical (ATC) Classification codes.

Prior medications and concomitant medications are defined as follows:

- Prior medications are those taken prior to the first dose date of double-blind study drug.
- Concomitant medications are those with a start date on or after the first dose date of double-blind treatment, or those with a start date before the first dose date of double-blind treatment and a stop date on or after the first dose date of study drug.

If a medication cannot be classified as “prior” or “concomitant” after applying imputation rules for missing/incomplete dates, it will be classified as concomitant.

Prior medications, prohibited medications (See Protocol Appendix B for the full list of prohibited medications defined in this study) taken during the double-blind treatment period, and concomitant medications taken during the double-blind treatment Period will be listed and summarized separately for the mITT population.

The number and percentage of subjects using each medication will be displayed together with the number and percentage of subjects using at least one medication within each therapeutic class (Anatomical Therapeutic Chemical [ATC]-Level 2), chemical subgroup (ATC-Level 4), and generic term.

7.5 Treatment Compliance and Exposure

Duration of exposure to double-blind study drug is defined as:

Date of last dose – Date of first dose + 1

For each subject, percentage of compliance is calculated as: total number of days taken study drug / the total number of days exposed to study drug. The total number of days on study drug can be calculated as: total number of days exposed to study drug minus the total number of days missing doses.

The number and percentage of compliant subjects will be presented for the Safety population, where compliant is defined as percentage compliance between 80.0% and 120.0% inclusive. The following percentage compliance categories will also be presented:

- <80.0%
- 80.0% to 120.0%
- >120.0%

Treatment duration (days) and percentage compliance will be summarized descriptively by treatment group for the Safety population.

- <28 days
- ≥28 days and <56 days
- ≥56 days and <84 days
- ≥84 days

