Subjects who meet all eligibility criteria, including UACR 200 to 3000 mg/g and eGFR ≥ 30 ml/min/1.73m² at both Visit 1 and Visit 2 and who also have $\geq 80\%$ study medication compliance during the 2-week placebo run-in phase, will be randomized at Visit 3 in a 1:1:1 ratio to 1 of 3 treatment groups: placebo, 40 mg of TMX-049, or 200 mg of TMX-049. Approximately 132 subjects will be randomized, with the expectation that 40 subjects per treatment group will complete 12 weeks of treatment and be included in the primary endpoint assessment. Randomization will be stratified by sUA (< 6.0 vs ≥ 6.0 mg/dL) and UACR (200 to < 300 mg/g vs 300 to ≤ 3000 mg/g) levels obtained at Visit 2. Study medication will be self-administered by the subject qd in the morning at about the same time each day and taken with food (breakfast or a snack), rather than on an empty stomach during the randomized treatment phase beginning on the day after Visit 3 and continued until the morning prior to Visit 6. The time of dosing and time of any food intake will remain consistent during the period of randomized treatment.

[figure not shown]
Randomized study participants will return to the site after 2 (Visit 4), 6 (Visit 5), and 12 weeks (Visit 6) of double-blind treatment. Study medication compliance will be assessed by pill count at each visit. First-morning void urine samples will be collected on 2 consecutive days prior to each visit. Urine and blood samples for determination of eGFR, sUA levels, and other laboratory tests will be obtained prior to and after initiation of randomized treatment. Results of sUA and UACR will not be reported to Investigators, subjects, and the Sponsor staff during the randomized treatment phase of the study. The time of PK sample acquisition, the time of dosing prior to the PK sample acquisition, and whether the subject took study medication with or without food will be recorded in the appropriate sections of the case report form (CRF) based on verbal communications with the subjects.

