7.4.1 Treatments Administered

All eligible subjects will receive qd doses of placebo during a 2-week placebo run-in phase. Subjects with $\geq 80\%$ study medication compliance during the 2-week placebo run-in phase will be randomized to receive qd doses of 40 mg TMX-049, 200 mg TMX-049, or placebo during the double-blind 12-week treatment phase.

On each dosing occasion, subjects assigned to the placebo group will swallow 1 tablet (placebo) and 2 capsules (placebo), subjects assigned to the low-dose group (40 mg TMX-049) will swallow 1 tablet (40 mg TMX-049) and 2 capsules (placebo), and subjects assigned to the high-dose group (200 mg TMX-049) will swallow 1 tablet (40 mg TMX-049) and 2 capsules (80 mg TMX-049) with water. All tablets/capsules making up a dose must be taken at the same time (ie dividing a dose is not permitted).

Treatment group	Capsule	Tablet
TMX-049 200-mg group	2 x 80-mg TMX-049 capsules	1 x 40-mg TMX-049 tablet
TMX-049 40-mg group	2 x placebo capsules	1 x 40-mg TMX-049 tablet
Placebo group	2 x placebo capsules	1 x placebo tablet

Subjects will be instructed to take study medication qd in the morning at approximately the same time each day. Subjects should take study medication with food, rather than on an empty stomach whenever possible, although occasional administration on an empty stomach is permissible. Subjects who don't usually eat breakfast should eat something (a snack would be acceptable), prior to dosing. Study medication will begin the morning after Visit 2 in the placebo run-in phase and the morning after Visit 3 at the beginning of the randomized treatment phase. The last dose of study medication will be taken in the morning before Visit 6.

If a subject does not take a dose of study drug within +12 hours of their regular dosing time, then the dose of study drug should be skipped and the subject should be instructed to take the study drug at the next regularly scheduled time. If a dose is missed, the site notified and recorded in the appropriate sections of the CRF based on verbal communications with the subjects. If a subject takes more than the intended dose,

they should report this to the site and an AE will be recorded if there were symptoms that accompanied the additional dose taken.

At Visit 4, subjects should not take study medication in the morning before their visit. Subjects can take study medication after the PK sample is obtained provided it is taken within +12 hours of their regular dosing time.

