5.5.1 Important Protocol Deviations Leading to Exclusion from the Per-Protocol Population

Type	Deviation	Method of Identification
Prohibited Medications	Subjects who have taken medications that are not permitted during the double-blind treatment period. A list of permitted and prohibited concomitant medication is provided in Appendix B in the protocol.	Manual review of blinded concomitant medications listing. [REDACTED] will provide the medical monitor with the list of concomitant medications taken by subjects. The medical monitor will review this list and note any prohibited medications. Subjects will be excluded if they were taking prohibited medications during the double-blind treatment period.
Noncompliance during 12-week double-blind treatment period	Subjects who had low study drug compliance (eg, repeated occurrence of compliance <80% during the double-blind treatment period)	Programmatic check based on the exposure and drug accountability data. Manual review will be performed for identifying subjects with low compliance rate during the double-blind treatment period.
Errors in Treatment Allocation	Subjects that received a wrong treatment at 1 or more study visits due to packaging or dispensing errors	Programmatic check based on unblinded IVRS database after the study is unblinded. The check will be done by comparing the bottle number that IVRS had assigned to the subject/visit against the bottle number actually used.
Clinical Trial Management System	[REDACTED] Clinical will provide the list of protocol deviations based on the clinical monitoring.	Manual review: The Sponsor will review this list and finalize any important protocol deviations which will then be included in the programming.

As defined in the table, the majority of the protocol deviations will be determined programmatically from the data. Those criteria which require clinical or medical monitoring interpretation will be reviewed prior to DBL, following discussion with the medical monitor and Teijin.

All the important protocol deviations leading to exclusion from the PP population occurring during the study will be reviewed and approved by Teijin prior to DBL and unblinding. Should other categories of important protocol deviations, not anticipated at the time of preparing this SAP, be identified during the study (and prior to unblinding), they will be documented in a separate document and included in all relevant protocol deviation reviews and approvals.

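### The compliance ratio in SAP 7.5 is capped at 100% and leaves out the pill count, so its >120% category is always empty and over-use or partial dosing cannot show

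*SAP*

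**What the plan says.** SAP 7.5 sets exposure as "Date of last dose – Date of first dose + 1". Compliance is "total number of days taken study drug / the total number of days exposed to study drug", and the numerator is obtained as "total number of days exposed to study drug minus the total number of days missing doses". The section then states that "compliant is defined as percentage compliance between 80.0% and 120.0% inclusive" and asks for three categories: below 80%, 80% to 120%, and above 120%. It adds that "Treatment duration (days) and percentage compliance will be summarized descriptively by treatment group for the Safety population", with four duration bands. It does not say where the missed days come from.

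Protocol 7.1 says "Study medication compliance will be assessed by pill count at each visit", and SAP 2.2 repeats this. Protocol 7.4.8 has sites reconcile what was dispensed against what came back. Under Protocol 7.4.1 a missed dose is "recorded in the appropriate sections of the CRF based on verbal communications with the subjects".

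SAP 5.5.1 removes subjects with low compliance from the Per Protocol population and gives as its example "repeated occurrence of compliance <80% during the double-blind treatment period". The stated method there is a programmed check on exposure and drug-accountability records, followed by manual review. It does not refer to the formula in 7.5.

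**The concern.** The formula and its reporting categories do not belong together. A band running to 120%, with a row above it, makes sense only for a measure that can register more drug used than was due. A count of units can do that; a count of days less missed days cannot. A reader who sees zero subjects above 120% in every arm would take it as a finding of no over-use, when the definition allows no other result.

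The formula also departs from the measurement that both documents name, and it works in whole days although a dose is one tablet plus two capsules. In the 200-mg arm the tablet carries 40 mg and the two capsules 160 mg, so a subject who takes only the tablet receives the active content of the 40-mg arm. The ratio has no means of showing this.

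Finally, the SAP's only compliance formula yields one figure per subject for the whole treatment period, whereas the example in 5.5.1 needs a value for each of several intervals.

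**Working it through.** The plan states no compliance result to reproduce; the check is of the definition.

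**Inputs**
- E = days from first to last dose, inclusive; m = missed-dose days (SAP 7.5).
- Units per daily dose: 1 tablet + 2 capsules = 3 (Protocol 7.4.1).
- Supply: 18 days per kit (Protocol 7.4.2.1), with 1, 2 and 3 kits dispensed at Visits 3, 4 and 5 (Protocol 7.5.4.2 to 7.5.4.4).
- Visit days 14 ± 4, 42 ± 7 and 84 ± 7 (Protocol Table 2).

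**1. Ceiling.** C = (E − m)/E = 1 − m/E. Since m cannot be negative, C cannot exceed 100%. Running every E from 1 to 104 days with every m from 0 to E − 1 gives a maximum of exactly 100.0% and no case above it. The 120% limit never operates.

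**2. The same bands under a unit count.** At nominal visit days, the most that could be counted as used is the whole supply:

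| Interval | Units dispensed | Units due | Maximum |
|---|---|---|---|
| Visit 3 to 4 | 1 × 18 × 3 = 54 | 14 × 3 = 42 | 128.6% |
| Visit 4 to 5 | 2 × 18 × 3 = 108 | 28 × 3 = 84 | 128.6% |
| Visit 5 to 6 | 3 × 18 × 3 = 162 | 42 × 3 = 126 | 128.6% |
| Overall | 324 | 252 | 128.6% |

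The category above 120% can then be reached.

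**3. Partial dosing.** Assume that a day with an incomplete dose is not entered as missed; the SAP gives no rule. Taking one unit of three every day scores 100% under SAP 7.5 and 1/3 = 33.3% by units. Two of three scores 100% against 66.7%.

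**4. Repetition.** Miss 3 of 14 days, then 6 of 28, then none of 42.
- Visit 3 to 4: 11/14 = 78.6%.
- Visit 4 to 5: 22/28 = 78.6%.
- Overall: (84 − 9)/84 = 75/84 = 89.3%.

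Two intervals fall below 80%, and the overall figure is comfortably compliant.

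**5. Early stopping.**
- Stop at Day 20, none missed: 20/20 = 100%.
- Stop at Day 20, five missed: 15/20 = 75.0%.
- Interrupt for 20 days and resume to Day 84: 64/84 = 76.2%.

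An early stopper therefore scores 100% only if no dose was missed before the last one.

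**6. Denominator for a unit count.** Nominal interval lengths will not do. With Visit 5 on Day 49 and Visit 6 on Day 77, both inside their windows, the last interval is 28 days. A fully adherent subject would score 28/42 = 67% against the nominal 42 days, but 28/28 = 100% against actual days.

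**The case against.** The strongest reply concerns the Per Protocol population. A reader might infer that, because the formula leans towards 100%, the screen at 80% leaves non-compliant subjects in that population. The documents do not support this. SAP 5.5.1 names drug-accountability data as a source, adds manual review, and never cites the 7.5 formula; a further row brings in deviations found by clinical monitoring. What stands is narrower: 5.5.1 gives no formula, interval length or number of occurrences for its example, and the one formula elsewhere in the SAP cannot supply them.

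A reader might also infer that the formula wrongly credits every early stopper with full compliance. Step 5 shows that this depends on earlier misses. Measuring adherence while on treatment is, moreover, a recognised convention. Early stopping is reported through the duration bands in the same section and through the discontinuation summary in SAP 7.2.

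Nor is it established that missed days rest on verbal report alone. SAP 7.5 names no source, and reconciled wallet counts could inform the missed-dose entries. Over-use is not wholly invisible either: Protocol 7.4.1 asks subjects to report taking more than intended, and returned packs are checked at Visits 4, 5 and 6. It is invisible in this ratio and in the table built on it.

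None of these replies touches the ceiling at 100% or the absence of units from the formula.

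**Conclusion.** The definition in SAP 7.5 is wrong as written. Its ceiling of 100% contradicts its own categories, and it omits the measure that Protocol 7.1 and SAP 2.2 name. The ceiling follows from algebra and needs no assumption. The partial-dosing gap (100% against 33.3%) assumes that incomplete doses are not logged as missed days. The repetition example (78.6% twice, 89.3% overall) is an illustration, not an expected frequency; the documents give no data on how often either pattern would occur.

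The reach is limited. The compliance table is descriptive, in the Safety population. The primary analysis in SAP 7.6.1 uses the mITT population and does not depend on compliance. Per Protocol membership is affected only in that its compliance criterion lacks a defined metric; the documents do not show that it inherits the 7.5 formula. The correction is worth making before database lock, so that the criterion is not settled subject by subject.

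**What to change.** In SAP 7.5, define compliance as (units dispensed − units returned) / (3 × actual dosing days between visits, ending at the last dose or treatment discontinuation), for each visit interval and overall. Dosing days should mean days on which a dose was due; say whether days of a permitted interruption count. Add a rule for wallets not returned, since otherwise their contents would count as taken.

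Use this measure for the three-category table, where the row above 120% then has a purpose. In SAP 5.5.1, refer to the per-interval values and state how many intervals below 80% make a repeated occurrence. Keep the days-based figure and the duration bands as exposure summaries, where early stopping belongs.

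The cost is SAP wording and one further derivation from accountability data already collected at Visits 4, 5 and 6. The drawback is the handling of unreturned packs, for which any rule is partly arbitrary and should be fixed before unblinding.
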